4.1 Objectives

a) Primary Objective:

1. **Appropriate shocks** as measured by shocks delivered for adjudicated sustained ventricular tachycardia (VT) or ventricular fibrillation (VF) episodes.
2. **Inappropriate shocks** as measured by shocks delivered for all episodes that are not adjudicated sustained VT or VF episodes.

The frequency and rate of appropriate and inappropriate shocks will be measured. The risk of receiving an inappropriate shock will be analyzed. The risk of not receiving appropriate shocks when necessary will also be analyzed.

b) Secondary Objectives

1. **Overall survival** as measured by the ratio of the number of patients that are alive at the end of the use of the WCD to the total population of patients prescribed the LifVest.
2. **Quality of life relative to health state** as measured through the administration of a patient quality of life survey. This survey has been used previously in a published study of patient quality of life.

5. Design of the investigation

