5.4 Monitoring plan

Authorized, qualified representatives of the sponsor will accomplish on-site monitoring during the study. The accuracy and completeness of core CRF data of a sufficient number of patients will be checked on site against source documents. Details will be given in a risk based monitoring plan.

Quality management will assure that medical data are subject of continuous plausibility checks and data cleaning. The primary outcome parameters consist of follow-up and arrhythmic event raw data which are directly transmitted in clinical routine from the WCD device to a central database to which the treating physician has access via an internet platform enabling him to review any potential arrhythmic event

detected by the device. These data are not modified by human interactions, thus being *per se* valid and do not require source data verification.

6. Statistical considerations and methods

This is a nonrandomized, multicenter observational study. All consecutive LifeVest patients will be asked to participate. Demographic data will be reported on all consenting patients. Thus, all patients in this study will receive LifeVest treatment. Descriptive statistics will be used to report major clinical characteristics of consenting patients, and incidence and frequency of appropriate and inappropriate shocks.

For the overall survival rate calculation, the population of reference will correspond to the total number of patients enrolled who were prescribed the LifeVest.

Standard methods will be used to calculate adjusted survival rates. Kaplan Meier survival curves will be used to report total mortality and wear time. The time to event and census are defined here after.

All reasons for therapy discontinuation will be reported in tabular form.

Event	Decision	Event date or census date
Occurrence of the event	Not censored	Date of the event occurrence
No event and patient followed until the study end	Censored	Date of WCD withdrawal
Lost-to-follow-up	Censored	Date of the last visit or last contact

It is common to use a significance threshold of 5%. This will be applied in this study.

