9.2 Follow-up data (wearing period) of ITT population

The following follow-up data will be described:

- Serious adverse events since inclusion by number of events in groups of
 - Type of event
 - Cardiac arrhythmic
 - Cardiac non-arrhythmic
 - Vascular non-cardiac (including stroke)
 - Cardiovascular without clearly defined other cause
 - Non-cardiovascular
 - Related hospital stay/prolongation of existing hospital stay
 - Causal relationship to WCD
 - Intensity
 - Outcome
 - Criteria for seriousness
- Time to first hospitalization
- Death
 - Cardiovascular
 - Cardiac
 - Vascular non-cardiac (including stroke)
 - Cardiovascular without clearly defined other cause
 - Non-cardiovascular
 - Death during prescription duration
 - Death while wearing the WCD
 - Death related to arrhythmic event
 - Death related to WCD dysfunction
- WCD events

WCD events/patients with WCD events with following event parameters:

- Type of event
- Termination of event
- Response button pressed
- Shock delivered
- Shock appropriate/inappropriate
- Occurrence of technical and non-technical problems during the wearing period
- Return of WCD device (end of therapy) due to:
 - Death
 - ICD implantation
 - Heart transplantation

- LV function improvement
- Patient's wish
- Other reason
- Clinical status on WCD return: Most recent LV-EF value, NYHA classification, risk assessment and if patient is still listed for heart transplantation
- Planned therapy after wearing period:
 - ICD implantation
 - PCI (Angioplasty, Stent)
 - Bypass surgery
 - Implantation of cardiac pacemaker
 - Heart transplantation
 - Implantation LVAD (left ventricular assist device)
 - Therapy with anti-arrhythmic agents
 - Other planned cardiac therapy
- Medication on WCD return

10. Primary analysis on ITT population

1. **Appropriate shocks** as measured by shocks delivered for adjudicated sustained ventricular tachycardia (VT) or ventricular fibrillation (VF) episodes.

- Quantitative analysis of appropriate shocks
- Analysis of the risk of not receiving appropriate shocks when necessary, calculated as number of non-terminated VT/VF events without shock delivery and without response button pressed/ number of VT/VF events

2. **Inappropriate shocks** as measured by shocks delivered for all episodes that are not adjudicated as sustained VT or VF episodes.

- Quantitative analysis of inappropriate shocks

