- The risk of receiving an inappropriate shock, calculated as number of inappropriate shocks/ non VT/VF events

11. Secondary analysis on ITT population

Overall survival as measured by the ratio of the number of patients that are alive at the end of the use of the WCD compared to the total ITT population.

Survival analysis using Kaplan-Meier curves and cox proportional hazard models will be performed to identify impacts on survival and the occurrence of WCD events will be displayed in tables in the following subgroups :

- indication for the WCD,
- medical history, and
- disease etiology: heart failure according to ESC guidelines
 - no HF (LV-EF $\geq 50\%$)

- intermediate HF (LV-EF $\geq 40 - < 50\%$)
- HF (LV-EF $< 40\%$)

12. Efficacy and safety analysis on ITT population

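### Overall survival is the share of patients alive when the vest is returned, so it has no time horizon; the planned Kaplan-Meier estimate, read at 30 and 90 days, should be the headline

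*Combined protocol and SAP*

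**What the plan says.** **The proportion.** Protocol 4.1 defines overall survival as a ratio: "number of patients that are alive at the end of the use of the WCD to the total population of patients prescribed the LifVest". SAP 4.2 repeats this, and SAP 11 applies it to the ITT set: "alive at the end of the use of the WCD compared to the total ITT population". Protocol 6 settles the denominator: "the population of reference will correspond to the total number of patients enrolled who were prescribed the LifeVest".

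**The length of observation.** Protocol 5.1.1 expects a mean wear of three months, with some indications at one month and others at up to six. Transplant candidates wear the vest until transplantation or an ICD. Under Protocol 5.2.8 participation stops when the vest is withdrawn. SAP 6.1 keeps every consenting patient in the ITT set whatever the wear time.

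**The curves.** Protocol 6 states: "Kaplan Meier survival curves will be used to report total mortality and wear time". Its table censors event-free patients at "Date of WCD withdrawal" and lost patients at "Date of the last visit or last contact". SAP 11 adds Cox models and subgroups by indication, medical history and etiology. It gives no other censoring rule and no time point at which survival is to be read.

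**Related pieces.** SAP 12.1 uses 30- and 90-day horizons from activation, but only for arrhythmic and shocked events. SAP 9.2 lists "Death during prescription duration" separately from deaths with the vest on; SAP 11 makes no use of that split.

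**The concern.** There are two separate problems, and they belong to two separate analyses.

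1. **The proportion has no horizon.** A patient who returns the vest after three days counts as a survivor on the same footing as one observed for six months. The result depends on mortality and on how long the vest was worn, and a reader cannot separate the two. Shorter wear alone raises it.

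2. **The Kaplan-Meier and Cox analyses have a time axis but may be informatively censored.** The listed reasons for return include ICD implantation, heart transplantation and improved LV function. Each could plausibly relate to the risk of death. The text available plans no sensitivity analysis for this and does not state the assumption.

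The study is meant to supply efficacy and safety data for a reimbursement renewal. A figure labelled overall survival on an ITT population is likely to be set beside other survival figures, and without a stated time it cannot be.

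**Working it through.** **Inputs.** Wear of 1, 3 and 6 months comes from Protocol 5.1.1. The documents give no mortality rate and no rate of return by risk, so every such rate below is an assumption.

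**The plan's own figure.** The only stated precision is for the shock rate with n = 550: 0.8 points at 1% and 1.8 points at 5%. It reproduces: 1.96 × √(0.01 × 0.99/550) = 0.83 points and 1.96 × √(0.05 × 0.95/550) = 1.82 points. It says nothing about survival, for which no figure is stated.

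**Step 1: sensitivity of the proportion to wear time.** With constant monthly mortality h and the same wear t for everyone, the share alive at return is exp(−h·t).

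| Assumed h per month | t = 1 | t = 3 | t = 6 | 1 minus 6 months |
|---|---|---|---|---|
| 0.5% | 99.5% | 98.5% | 97.0% | 2.5 points |
| 1% | 99.0% | 97.0% | 94.2% | 4.8 points |
| 2% | 98.0% | 94.2% | 88.7% | 9.3 points |

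Mortality is identical within each row, so the differences come from wear time alone.

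**Step 2: what censoring at return could do to Kaplan-Meier.** Assume half the patients die at 0.5% per month and half at 3%.

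- True survival at 3 months: 0.5·exp(−0.015) + 0.5·exp(−0.09) = 94.95%.
- True survival at 6 months: 0.5·exp(−0.03) + 0.5·exp(−0.18) = 90.3%.

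Let the two groups return the vest at constant rates c₁ and c₂ (1 divided by mean wear). Kaplan-Meier then tends to exp(−∫h̄(t)dt), where h̄(t) is the average hazard among those still wearing it: h̄(t) = Σhᵢ·exp(−(hᵢ+cᵢ)t) / Σexp(−(hᵢ+cᵢ)t). The proportion alive at return is 0.5·c₁/(c₁+h₁) + 0.5·c₂/(c₂+h₂).

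| Return pattern (mean wear) | Kaplan-Meier, 3 months | Kaplan-Meier, 6 months | Alive at return |
|---|---|---|---|
| Unrelated to risk (3 months for all) | 94.95% | 90.3% | 95.1% |
| Low risk returns first (1 v 6 months) | 93.1% | 85.3% | 92.1% |
| High risk returns first (1 v 6 months) | 96.8% | 95.1% | 97.1% |
| Low risk returns first (2 v 4 months) | 94.3% | 87.9% | 94.15% |
| High risk returns first (2 v 4 months) | 95.6% | 92.6% | 96.2% |

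Kaplan-Meier is unbiased when return does not depend on risk. Otherwise it can err in either direction, and in each of these scenarios the error is smaller at 3 months than at 6. The proportion varies as well and has no time attached in any row.

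**The case against.** **The quantity is legitimate and its definition is open.** Survival while bridged by the device is a fair description for a secondary objective in an uncontrolled study, and each definition says what is counted. SAP 6.1 explains that ITT here means consenting patients who meet the criteria. This stands: the proportion can stay. What does not stand is calling it overall survival with no time attached.

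**A reader might infer a spurious difference of 4.8 points between indications.** The documents do not support that. SAP 11 defines the proportion for the whole ITT population and uses Kaplan-Meier and Cox for indications. With identical constant hazards those methods would show no difference between indications. The 4.8 points illustrate sensitivity only.

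**A reader might infer that the curves are flattering.** That too goes beyond the text. A link between return and prognosis is plausible but not stated, and deterioration is not a listed reason for return. Early return after LV improvement would push Kaplan-Meier down rather than up.

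**A reader might infer that deaths after return are already recorded and ignored.** The prescription-period item in SAP 9.2 sits under a heading limited to the wearing period, and may only separate deaths with the vest off from deaths with it on. SAP 5 plans follow-up to 31 March 2019 without saying whether vital status is collected after return. The national cause-of-death lookup in Protocol 5.2.3 covers only patients lost to follow-up.

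**Part of the ground is covered.** Reasons for ending use are already reported (Protocol 6; SAP 9.2 and 14), so nothing more is needed there. Patients with under 8 days of wear are evaluated separately (Protocol 5.2.3; SAP 13), although they remain in the ITT proportion.

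**Conclusion.** The point holds in two parts of unequal strength.

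The missing horizon follows directly from the definition and the range of wear times. Its size depends on mortality, which the documents do not give: over assumed rates of 0.5% to 2% per month, moving everyone from 1 to 6 months of wear changes the proportion by 2.5 to 9.3 points.

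The censoring problem is a possibility, not a finding. It rests on the inference that return is related to prognosis. Under the two-group assumptions above, Kaplan-Meier at 6 months could be about 5 points too low or too high (85.3% or 95.1% against 90.3%), and it is correct if return is unrelated to risk.

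Neither part invalidates the study or touches the shock endpoints. The reporting should be changed because the better estimate is already planned and lacks only a time point, a label and a stated assumption.

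**What to change.** 1. In SAP 4.2 and 11, keep the proportion but label it *alive at end of WCD use*.
2. Make the headline survival result the Kaplan-Meier estimate with 95% confidence interval at 30 and 90 days from activation, overall and by indication, with numbers still at risk.
3. Describe that result as survival during WCD use. Put the censoring rule in the SAP, and state that it assumes return is unrelated to the risk of death.
4. Say what the prescription-period death item in SAP 9.2 covers. If vital status after return is in fact available within the prescription period, add a sensitivity analysis that counts those deaths as events. Prescription length varies, so this too should be read at 30 and 90 days.

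**Cost.** Items 1 to 3 are SAP wording and reading an already planned curve at two times; they need no new data. Fixed horizons do not remove informative censoring, which is why the assumption must be stated. The headline figure may be slightly less favourable. Precision at 90 days will be lower where few patients still wear the vest: if wear were exponential with a mean of three months, about exp(−3/3) = 37% would remain, or roughly 440 of 1,200, and fewer in each indication.

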6.1 Sample size

This study is a post-inscription study designed to describe all patients treated by LifeVest in a comprehensive way. Thus this study will be proposed to all patients receiving LifeVest.

No sample size calculation has been planned. All patients accepting to participate will be included.

The LifeVest device is commercialized in France since approximatively 1 year, the number of subjects has been estimated based on the sales and the foreseen participation rate.

It is estimated that approximately 1,700 patients will receive LifeVest in clinical routine between May 2015 and April 2018 (300 patients first year, 520 patients second year and 880 patients third year of marketing) in France. After obtaining all regulatory approvals, the study is expected to start in August 2016. Between August 2016 and April 2018, 1,110 patients would receive LifeVest in clinical routine. Considering a participation rate of 50% related to centers participating in the study and consent given, around 550 patients will participate in this study.

According to most recent data, the frequency of shock delivery is expected to be between 1% and 5 %. In this present study, 550 patients will allow for assessing a treatment rate ranging between 1%-5% with

an absolute precision < 2% (0.8 for 1% and 1.8 for 5%). Therefore, this sample size would be sufficient to answer the research questions.

6.2 Patient Survey

All survey data will be included in the analysis as long as the patient answered at least one item on the survey. In other words, no exclusion criteria will be used based on survey response completeness. Overall survey statistics will be presented for the survey data results including overall response rate, item level response rate, Survey responses for all items will be analyzed and reported. The majority of the items on the survey ask the patient to indicate their agreement using the 5-point Likert agreement response scale (Strongly agree, Agree, Neither agree nor disagree, Disagree, Strongly disagree) with the following topics regarding their use of the LifeVest:

- Ease of use
- Peace of mind
- Worry
- Worry about being alone
- Confidence in physician knowledge about managing condition
- Sleep quality
- Confidence returning to activities of daily living (screened)
- Confidence to exercise or perform cardiac rehabilitation (screened)
- Improved self-care
- Taking condition seriously
- Family and caregiver peace of mind
- Family and caregiver sleep quality

Patient information collected on the survey will include basic demographic information for subgroup analyses as well as patient self-reported health status from the SF-12. Consistent with previous publication, survey responses for items using the 5-point Likert agreement response scale will be presented as the top two box or the percentage of patients that either Strongly agree or Agree with the statement in the survey item.

7. Procedures used for data review, database cleaning, and issuing and resolving data queries

All medical data in this study are to be recorded directly in an e-CRF system (MARVIN) running on a single central server. The e-CRF system is available for all participants based on individual access codes (numerical code) according to their duties and responsibilities in the project 24 hours/7 days. The investigator must ensure the accuracy, completeness and timeliness of data.

Plausibility rules and alert levels for parameters are programmed in the e-CRF system ensuring an optimized level of first-line data quality. Manual data queries based on repetitive statistical analyses will additionally improve data completeness and quality.

7.1 Procedures for verification, validation and securing of electronic clinical data systems, if applicable.

The e-trial management system MARVIN used in this study is a GCP and 21 CFR 11 compliant EDC and CDM system based on the CDISC ODM data standard.

Any change or correction to an e-CRF will automatically be tracked (Audit Trail), recording the account ID of the person being logged in as well as the time stamp of the change. The e-CRF system will not accept changes without given reason. The history of changes to a single item including original entries is always available.

8. Amendments to the study protocol

Any amendment to the study protocol must be approved by the Sponsor. A study protocol amendment may not be implemented until after it has been sent for comment to the IEC responsible for the principal investigator. Since the study comprises only procedures routinely undertaken, no immediate implementation of changes necessary for patient safety are expected.

9. Deviations from study protocol

Deviations from the study protocol are not to be expected, because this is only an observational study without predefined procedures:

10. Statements of compliance

10.1 Statement specifying that the clinical investigation shall be conducted in accordance with the ethical principles that have their origin in the Declaration of Helsinki

The procedures set out in this study protocol are designed to ensure that the Sponsor and the Investigator abide by the principles of ISO 14155:2011 and the Declaration of Helsinki (latest version) concerning the conduct, evaluation and documentation of the clinical investigation.

10.2 Statement specifying compliance with this International Standard and any regional or national regulations, as appropriate.

The study procedures will also be performed adhering to the local legal conditions and regulations and to the applicable regulatory requirements. Each Investigator must confirm this by signing the study protocol. The text of the applicable version of the Declaration of Helsinki will be provided by the Sponsor.

This study is within the scope of Chapter IX, relating to the treatment of personal data for research purpose in the field of health, of the French Law No. 2004-801 of 6 August 2004 amending laws No. 78-17 of 6 January 1978 and No. 94-548 of 1 July 1994 relating to information technology, files and freedoms.

The protocol will be submitted for review to the Advisory Committee on Information Processing in Research in the Field of Health (Comité Consultatif sur le Traitement de l'Information en Matière de Recherche dans le Domaine de la Santé - CCTIRS), then for approval to the French Data protection Authority (Nationale Informatique et Liberté - CNIL) before any data collection.

The participating investigators receiving financial compensation for the conduct of the study, the protocol and the financial agreement will be sent for review to the French Medical Council (Conseil National de l'Ordre des Médecins - CNOM) in accordance with the Article L.4113-6 of the French Code of Public Health.

10.3 Statement specifying that the study protocol will be sent for comment to the EC

In accordance with the French legislation (Articles L.1121-1 and following of the French Code of Public Health), given that the physician-patient relationship is not changed and that no examination or consultation is specific to the observatory, the study will not be subject to the opinion of a French Ethics Committee (Comité de Protection des Personnes, CPP).

10.4 Statement specifying the type of insurance that shall be provided for subjects, if appropriate.

No insurance is required because this study is purely observational. All medical treatment is decided and provided in clinical routine. The clinical routine insurance of the product will therefore cover all risk.

11. Informed consent process

Before entering into the study, information about the intention and nature of the study will be provided to each potentially eligible patient by the prescribing responsible physician of each participating center. Each patient will be informed about the use of his medical data in the clinical study according to the requirements data privacy regulations, i.e. consent to processing medical data of the patient to a central scientific database. Sufficient time will be allowed for the information to be read and for questions to be asked. Only subjects able to give their informed consent will be enrolled in this clinical study.

The patient must be told that withdrawal of informed consent to use their data in the clinical study is possible at any time, without stating a reason and without prejudice, and does not cause any disadvantages.

The patient will in any case receive detailed training on the use of the WCD by the ZOLL Company personnel. This will give the patient the opportunity to raise further questions about the device and data handling to the ZOLL personnel and the responsible physician.

12. Adverse events, adverse device effects and device deficiencies

Serious adverse events, i.e. cardiac and non-cardiac death, hospitalization, heart surgery, will be documented in the e-CRF. Adjudication of SAEs and second assessment of safety aspects will be performed by the sponsor.

Non-serious adverse events and adverse device effects as well as serious adverse device effects and other device deficiencies, as defined by good clinical practice and other relevant regulations, will be reported according to clinical routine procedures. For all legal reporting requirements, the sponsor remains fully responsible in the frame of his regular routine processes of reporting concerning his market authorization. Therefore, the sponsor's assessment and reporting responsibilities are not affected by this study.

13. Clinical Event Committee

The Clinical Event Committee will be composed of three experts. These experts will adjudicate, in an independent blinding manner, the occurrence of treatments and their classification (appropriate/inappropriate shocks), and will review the detected arrhythmia where no treatment was given.

14. Study limitations

Study limitations include mainly the observational nature of the design and the lack of control group.

The number of included patients could also be a limitation. As the study will start along with the early-stage launch of LifeVest, the number of patient inclusions will depend on the commercialization activities and is expected to increase over time.

15. Quality control & Quality assurance

The accuracy and completeness of the CRF entries will be monitored and checked against source documents according to a risk based monitoring plan.

Quality control procedures will be implemented to ensure the relevance and consistency of datasets.

16. Publication policy

16.1 Statement indicating whether the results of the clinical investigation will be submitted for publication.

